## **Specific Aims and Hypotheses**

#### Specific Aims and Hypotheses

#### Primary Outcome Measure:

(1) Cannabis withdrawal (mood, sleep quality and duration, food intake)

(2) Cannabis relapse defined as (1) time to any MJ use as recorded by the timeline follow back method and

confirmed by urine metabolite levels, or (2) time to dropout, whichever comes first, and (3) medication compliance (% of pills taken) or time to discontinuation. Participants who relapse will continue in the trial to obtain secondary outcome measures.

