Study: # 7343 entitled EFFECT OF CLONAZEPAM ON CANNABIS WITHDRAWAL AND RELAPSE IN TREATMENT-SEEKING PATIENTS: COMBINED INPATIENT/OUTPATIENT STUDY

PI: [name].

NCT# NCT02913924

Statistical Analysis Plan (Grant): 9/19/2013

Amended 4/15/2016 (DSMP)

Grant Submission U54 DA037842: 9/19/2013

3. Data Analysis a. Outcome Measures and Covariates

i. Primary outcome measures: 1) Cannabis use: The time to sustained relapse defined as 5 days of cannabis use over a 7 day period as recorded by the Timeline Followback method and confirmed by creatinine-normalized quantitative urine THC levels, or time to dropout of study, whichever comes first (survival outcome).

ii. Secondary outcome measures: These measures are designed to capture changes in cannabis consumption patterns and other symptoms not measured by the primary outcome measures.

1) Abstinence during the final two weeks (study weeks 11 and 12) of the study (dichotomous)

2) Retention in treatment (survival outcome)

3) Days per week of cannabis use (continuous longitudinal)

4) Cannabis withdrawal: measured by weekly Marijuana Withdrawal Checklist (continuous longitudinal)5) Cannabis craving: measured by weekly Marijuana Craving Questionnaire (continuous longitudinal)

6) Sleep disturbance: measured by the Medical Outcomes Study—Sleep Scale (continuous longitudinal)

iii. Covariates: 1) Demographic characteristics (e.g., gender, age) 2) Baseline severity of cannabis use (measured by the quantity of cannabis per using day at baseline)

iv. Other measures: Adverse effects, as measured by the Systematic Assessment for Treatment and Emergent Events (SAFTEE), will be assessed, including potential effects on compliance and outcome.

b. Sample Size and Randomization: The Research Core will supervise randomization procedures. A total of 72 patients will be recruited over a 2.5-year period and randomized to the double-blind treatment trial, with 36 patients randomized to each of the two treatment groups, nabilone/XR-NTX arm and placebo arm. The randomization sequence will be balanced in blocks of random size (2, 4, 6) to prevent clinicians from guessing what the next patient's treatment might be.

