d. Significance Testing and Preliminary Analyses: All tests for main effects will be performed at twotailed significance α =5%. Before performing specific analyses (described below), we will examine all variables for outliers. The distributions of all continuous variables will be checked for normality, and transformations will be employed, if necessary, before applying specific parametric techniques. The distribution of demographic variables (ethnicity, gender, age) and other covariate measures of at baseline in the treatment arms will be examined and described in terms of means, standard deviations, proportions and 95% confidence intervals. The covariates (specified in Section 3.a.iii) may be associated with treatment outcome. For this reason, we will adjust for these covariates in all models used to test the study hypotheses. These covariates will be included in all models as main effects regardless of their statistical significance or whether they differ between treatment groups. In the secondary analyses, we will adjust also for baseline value of the outcome variable where appropriate. This adjustment will be based on the inclusion of main effects for the baseline.

e. Hypotheses Testing i. Primary hypotheses:

Hypothesis 1: Nabilone and XR-NTX will significantly increase time to relapse as compared to placebo. The following Cox Proportional Hazards model will be used: (1) $\log{hi(t)} = \log{h0(t)} + \beta 1 I J + \beta 2 U J J$ where hij(t) is the hazard for individual i in the treatment group j at time t; h0(t) is the baseline hazard function; Uj is the vector of covariates; and I J is the indicator variable for treatment with nabilone and XR-NTX. Significant I J indicates that the hazard rate of each treatment group is different. ii. Secondary hypotheses:

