Hypothesis 5: Over time, subjects in the nabilone and XR-NTX group will experience significant reduction in the pattern of cannabis withdrawal symptoms (measured as mean Marijuana Withdrawal Checklist score per week) compared to the subjects in the placebo group.

Hypothesis 6: Over time, subjects in the nabilone and XR-NTX group will exhibit significantly reduced cannabis cravings (as measured by Marijuana Craving Questionnaire) compared to subjects in the placebo group.

Hypothesis 7: Over time, subjects in the nabilone and XR-NTX group will experience significantly less sleep disturbance (as measured by the Medical Outcomes Study Sleep scale) compared to subjects in the placebo group. To test the secondary hypotheses 5, 6, and 7 we will use the same model as in (3) where Yijt is the appropriate outcome variable (as specified for each hypothesis) for the i th subject in the treatment group j at week t (t =1, 2, ..., 12). We will first test the interaction effect of group and time as described for Hypothesis 4.

iii. Exploratory Analyses We will explore whether there are differences between the two groups with respect to the number of adverse effects, side effects, and tolerability in relation to the primary outcome. We will also explore whether co-occurring psychiatric disorders, gender, concurrent treatment exposure, trauma history, or impulsivity are predictors of treatment outcome.

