f. Power Analysis: The sample size of 72 was chosen to ensure sufficient power (at least 80%) of a twosided test with level of significance α =0.05 for detecting difference between the two experimental treatments with respect to time to relapse, based on the Cox proportional hazards model. We expect that the nabilone and XR-NTX group will have greater time to relapse than the placebo group. The rate of retention for the placebo group at 12 weeks can be expected to be 15% based on our prior studies. With 36 per arm, we will be able to detect a difference in retention (without relapse) rates between placebo versus nabilone and XR-NTX of approximately 25% (i.e. 15% on placebo vs 39.6% on nabilone and XR-NTX). This corresponds to a hazard ratio of 0.49 (Machin et al. 1997). The proposed sample size will also enable us to estimate the retention rate of the treatment group with a 95% confidence interval, ±15%, in the worst case. The computation above was performed assuming that the covariates (i.e., baseline cannabis use and age) do not have a predictive power. The 25% rate difference is consistent with a medium to large sized effect, which is what we are seeking in this early Phase II trial. This represents an effect that would be clinically meaningful and likely to make a substantial impact on the success of XR-NTX treatment in clinical practice A2. Primary and Secondary Outcome Measures Primary Outcome Measure: (1) Cannabis withdrawal (mood, sleep quality and duration, food intake) (2) Cannabis relapse defined as (1) time to any MJ use as recorded by the timeline follow back method and confirmed by urine metabolite levels, or (2) time to dropout, whichever comes first, and (3) medication compliance (% of pills taken) or time to discontinuation. Participants who relapse will continue in the trial to obtain secondary outcome measures. Secondary Outcome Measures: (1) Abuse liability (medication liking, desire to take again) (2) Cognitive task performance (3) Side effects and tolerability.

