A4. Power calculation and sample size Cannabis Withdrawal. We hypothesize that clonazepam will decrease symptoms of cannabis withdrawal (e.g. ,irritability, sleep efficiency). With a sample size of 80, the test of a single contrast at the 0.050 level will have >90% power to detect a 25% decrease in these ratings under conditions of medication administration compared to placebo, assuming the same between-level correlation and SD than our earlier studies. Cannabis Relapse: The time to relapse as recorded by the Timeline Follow Back method and confirmed by creatinine-normalized quantitative urine THC levels, or time to dropout of study, whichever comes first (survival outcome). The sample size of 80 was chosen to ensure sufficient power (at least 80%) of a two-sided test with level of significance 5% for detecting difference between the two experimental treatments with respect to time to relapse, based on the Cox proportional hazards model. We expect that the clonazepam group will have greater time to sustained relapse than the placebo group. The rate of survival for the placebo group can be expected to be 15% based on our prior studies. With 40 per arm, we will be able to detect a difference in proportion of surviving in placebo versus clonazepam of approximately 27% (i.e. 15% on placebo vs 41.81% on clonazepam). This corresponds to a hazard ratio of 0.46 (Machin et al. 1997). The power computation was performed assuming that the covariates (i.e., baseline cannabis

use and age) do not have any predictive power. If they do, the power of the primary hypothesis will be higher than 80%. The 26.81% rate difference is consistent with a medium to large sized effect, which is what we are seeking in this early Phase II trial. This represents an effect that would be clinically meaningful and likely to make a substantial impact on the success of clonazepam treatment in clinical practice. The proposed sample size n=40 for clonazepam group will also enable us to estimate the relapse and retention rates of the treatment group with a 95% confidence interval, $\pm 15.5\%$, in the worst case.

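### The SAP filed for the clonazepam trial carries two incompatible primary relapse definitions, and no sentence says that the one written for other drugs is superseded

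*SAP*

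**What the plan says.** **SAP section 3.** The SAP is headed for the clonazepam study. Section 3.a.i gives a single primary outcome, "The time to sustained relapse defined as 5 days of cannabis use over a 7 day period", with dropout also an event. Section 3.a.ii makes withdrawal secondary. Section 3.b describes 72 patients, "with 36 patients randomized to each of the two treatment groups, nabilone/XR-NTX arm and placebo arm". The relapse model is introduced in 3.e with "The following Cox Proportional Hazards model will be used", and its treatment indicator is nabilone and XR-NTX. Hypothesis 7 in the same section concerns "sleep disturbance (as measured by the Medical Outcomes Study Sleep scale"), an instrument that does not appear in the protocol's Table 3.

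**SAP A2 and the protocol.** The protocol's Primary Outcome Measure list reads "Cannabis relapse defined as (1) time to any MJ use as recorded by the timeline follow back method", or dropout if earlier, and A2 repeats it. Both list "Cannabis withdrawal (mood, sleep quality and duration, food intake") as primary. Both also put medication compliance in that list, although Study Procedures in the protocol calls adherence and tolerability secondary.

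**SAP A4.** This is the clonazepam power text: 80 patients, 15% versus 41.81% surviving, hazard ratio 0.46, two-sided 5%, at least 80% power. It first calls the endpoint time to relapse and later time to sustained relapse.

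**SAP C3.** It plans repeated-measures ANOVA for subjective effects, food intake, sleep and task performance. It names longitudinal mixed models for the primary outcome variables. It does not mention a Cox model.

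**The concern.** The relapse endpoint decides who has an event and when. With two definitions under one study header and no statement of precedence, an analyst could cite the filed SAP for either, including after seeing the data. The status of withdrawal changes with the same choice.

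Section 3 can be neither followed nor simply dropped. It names other drugs, another sample size and an instrument this trial does not schedule. Yet the written-out Cox model, the commitment to adjust every model, the full covariate list and the block randomization are found only there. The power statement is affected too, because a placebo event-free rate and a hazard ratio belong to one particular event.

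**Working it through.** **1. The two events compared.** Any episode of 5 days of use in 7 contains a first day of use, and dropout counts under both definitions. So the any-use event comes no later than the sustained event, and the any-use event-free rate is equal or lower.

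- A participant who uses on one day and then abstains to week 12 has an event under A2 and the protocol, and none under section 3.
- The protocol's Study Procedures start relapse measurement on day 6. An any-use event can fall on day 6. Five days of use need days 6, 7, 8, 9 and 10, so the earliest use-based event is day 10.

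**2. A4's figure reproduced.** Inputs from A4: 40 per arm, 15% versus 41.81%, two-sided 5%.

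- Hazard ratio = ln(0.4181)/ln(0.15) = 0.4597, stated as 0.46.
- Events = 40 × (0.85 + 0.5819) = 57.3.
- Freedman power = Φ(√57.3 × (1 − 0.4597)/(1 + 0.4597) − 1.96) = 80.0%.

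The arithmetic is sound. (Schoenfeld's formula gives 83.7%.)

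**3. Which event does the 15% describe?** Section 3.f, where relapse means 5 days in 7, says "The rate of retention for the placebo group at 12 weeks can be expected to be 15% based on our prior studies". A4 says "The rate of survival for the placebo group can be expected to be 15% based on our prior studies" and does not name the event. The figure is the same in both places, and the documents do not say which endpoint the prior studies used.

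**4. Power for any use over a range.** The documents give no separate any-use rate. The 10% and 5% rates and the hazard ratios 0.50 and 0.55 are therefore assumptions. Clonazepam event-free rate = (placebo rate)^HR; events = 40 × (2 − placebo rate − clonazepam rate); power by Freedman as above.

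| Placebo event-free | HR 0.46 | HR 0.50 | HR 0.55 |
|---|---|---|---|
| 15% | 80% (57.3 events) | 72% (58.5) | 61% (59.9) |
| 10% | 83% (62.1) | 76% (63.4) | 65% (64.7) |
| 5% | 86% (67.9) | 79% (69.1) | 68% (70.3) |

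Down each column power rises, because there are more events. Every value below 80% comes from a weaker assumed hazard ratio.

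**5. Section 3.f checked before any reuse.** Inputs: 36 per arm, 15% versus 39.6%. Hazard ratio = ln(0.396)/ln(0.15) = 0.488. Events = 36 × (0.85 + 0.604) = 52.3. Freedman power = 70% (Schoenfeld 74%), not the stated 80%. That statement should not be carried over with the drug names changed.

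**6. Withdrawal measure.** Study Procedures measures withdrawal on inpatient days 2–5. Outpatient Study Assessments calls the Marijuana Withdrawal Checklist the primary measure of withdrawal and the Pittsburgh index the primary outcome for sleep. Table 3 schedules both weekly in the outpatient phase.

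**The case against.** The best defence is that section 3 is recognisably grant text for other drugs. The header carries a 2013 grant date and a 2016 amendment date, every block that names clonazepam or 80 patients lies outside section 3, and A2 matches the protocol. On this view only one stray word in A4 needs correcting. Much of this stands: the two definitions are not of equal standing, and any use is the likely intent. But neither date is tied to a section, no sentence retires section 3, and the stray word sits in the clonazepam power text itself.

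A reader might also infer that the clonazepam text has no survival analysis at all. It does not go that far. A4 calls relapse a survival outcome, bases its test on the Cox model, mentions baseline cannabis use and age as covariates, and counts dropout as an event. C3 states intention to treat. What is missing outside section 3 is the written-out model, the commitment to adjust, the full covariate list and the randomization scheme. C3's mixed models for the primary outcomes do not match the Cox test that A4 powers.

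**Conclusion.** The conflict is real and should be resolved before unblinding. The plan as filed supports two different primary relapse events. A2 and the protocol point to any use, but the SAP does not say so and A4 uses both terms. The 80% power reproduces by Freedman's formula and belongs only to whichever endpoint the 15% and 0.46 describe.

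Two stronger readings are tempting and not supported:

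- *That 80 patients are too few for the any-use endpoint.* At hazard ratio 0.46, an any-use event-free rate below 15% raises power. A shortfall needs a weaker any-use effect, which the documents neither give nor imply.
- *That type I error is inflated because A4 plans two 5% tests, one for withdrawal and one for relapse.* The protocol's Background section sets these out as two aims, and no passage makes one overall claim from either. If each aim carries only its own claim, each is tested at 5% and nothing need change. A family-wise error of up to 1 − 0.95² = 9.75% (independent tests) arises only if either alone may support one overall claim. This is a detail to state, not part of the main finding.

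**What to change.** 1. Replace section 3 with text for this trial: clonazepam and placebo arms, 80 patients, hypotheses, Cox model for relapse, covariates and randomization. Make C3 name the Cox model for relapse. Do not carry over section 3.f's power statement.
2. Use the protocol's definition, time to any use or dropout, as the primary relapse endpoint throughout. Report relapse defined as 5 days in 7 as a secondary or sensitivity analysis.
3. Establish first which endpoint the 15% and 0.46 come from. Only then correct the word sustained in A4; deleting it earlier could mislabel the basis of the power. If they are not any-use figures, restate the power.
4. Reconcile the status of compliance between the primary outcome list and Study Procedures, and the withdrawal measure and time window between the inpatient days and the outpatient scales.
5. As a side note, state before unblinding whether withdrawal and relapse each carry only their own claim.

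The cost is wording, plus one power calculation if the inputs prove not to be any-use figures. If the any-use hazard ratio is then judged weaker than 0.46, power at 80 patients may fall below 80%, and the SAP should say so.

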## **Study Procedures**

Describe the procedures required for this study

*Study Participants*: Participants will be 80 men and nonpregnant women with CUD who report using cannabis a minimum of 5 days per week over the past 28 days. The minimum threshold of a near-daily pattern of cannabis use will select a population with moderate-to-severe CUD. This level of severity is consistent with the sample in our previous clinical trial (Levin et al. 2011), and, we suspect, typical of individuals with CUD who seek treatment. This sample is less likely to achieve abstinence spontaneously or in response to non-medication aspects of the trial (e.g., general therapeutic support), and thereby minimize the placebo response rate. Selecting for near-daily cannabis users will also prevent a "floor effect" (i.e., participants using cannabis infrequently at baseline would be unlikely to demonstrate significant improvement).

**Inpatient phase**: Patients seeking cannabis treatment will move into the inpatient unit at NYSPI for 5 nights. On move-in day, participants will only receive the PM capsule administration; all capsules will be given under observation and will be double blind. During the next 4 days (days 2-5; Table 1), we will measure medication effects on cannabis withdrawal, including measures of mood, cannabis craving,

objective and subjective measures of sleep, and food intake in our Outpatient Marijuana Laboratory. Cannabis relapse measures will begin following discharge on day 6.

**Outpatient phase**: After discharge from the inpatient phase, 12-weeks of outpatient treatment will be conducted (Table 2). Study visits will occur twice weekly. One visit per week will be with the research psychiatrist for a Medical Management session to perform study assessments and to monitor medication effects and compliance. Participants will have a manual-guided (Pettinati et al. 2005) supportive behavioral treatment session with the research psychiatrist each week. This psychosocial intervention facilitates compliance with study medication and other study procedures, promotes abstinence from cannabis and other substances, and encourages mutual-support group attendance. The second visit each week will be for vital sign monitoring, urine toxicology and completion of self-report measures. Participants will be given cash incentives contingent on study visit attendance and completing other study procedures with the objective of achieving a high treatment adherence.

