## Table 3: Outpatient Study Assessments

	X once weekly; XX twice weekly	Screening	Baseline	Week 1	Week 2	Week 3	Week 4	Week 5	Week 6	Week 7	Week 8	Week 9	Week 10	Week 11	Week 12
	Medical History and Physical Examination	x													
	Pregnancy, serum	x													
	Pregnancy, urine		x				х				х				х
	Psychiatric Evaluation	x													
5	Serum Laboratory Examination	x					х				х				х
latic	Urinalysis	x					х				х				х
Medical Evaluation	Urine Toxicology	x	x	х	X X	x x	x x								
dical	Urine Fluorometry (quantitative riboflavin)			x	X X	X X	x x								
Med	Vital signs (weight, pulse, blood pressure, and temperature)		x	x	X X	x x	x x								
	CIWA-BZD									Х	Х	Х	Х		
	Clinical Global Improvement Scale (CGI)- Observer		x	х	x	x	х	х	x	x	х	x	х	x	x
	C-SSRS	x	x		x		х		х		х		х		х
	Hamilton Anxiety Scale (HAM-A)		x		x		х		х		х		х		х
Interview	MINI International Neuropsychiatric Interview	x													
ter	Structure Pill Count Interview			х	x	x	х	х	х	x	х	х	х	х	х
_	Systematic Assessment for Treatment and Emergent Events (SAFTEE)		x	x	x	x	x	x	x	x	x	x	х	x	x
	Timeline Follow-Back (TLFB)	x	x	х	x	x	х	х	х	x	х	х	х	х	х
	Treatment Services Review (TSR)		х	х	x	x	х	х	х	x	х	х	х	х	х
	Clinical Global Impression (CGI)-Self		x	х	x	x	х	х	x	х	х	х	х	х	х
Self- Report	Marijuana Craving Questionnaire (MCQ)		х	х	x	x	х	х	х	x	х	х	х	х	х
Se Rep	Marijuana Withdrawal Checklist (MWC)		x	х	x	x	х	х	x	x	х	х	х	х	х
	Pittsburgh Sleep Quality Index (PSQI)		х	х	х	х	х	х	х	х	х	х	х	х	х

Tabl	e 1: Inpatient F					
Day	1	2	3	4	5	6
Study Groups	Move-in	Witha	Irawal, cognition	, abuse liability		Move-out
Clonazepam (mg/day)	1.0	2.0	2.0	2.0	2.0	2.0
Placebo (mg/day)	0.0	0.0	0.0	0.0	0.0	0.0

Study Groups	Week 1 Days 6-7 (outpatient)	Weeks 2-7 Days 8-49 (outpatient)	Week 8 Days 50-51 (outpatient taper)	Week 8 Days 52-54 (outpatient taper)	Week 8 Days 55-56 (outpatient taper)	Week 9-12 Days 57-84 (outpatient obervations)
Experimental Group	clonazepam capsules 1 mg twice daily	Clonazeapam capsules 1 mg twice daily	Clonazepam capsules 0.5 mg QAM and 1 mg QHS	Clonazepam capsules 0.5 mg QAM and 0.5 mg QHS	Clonazepam capsules 0.5 mg QHS	No study medication
Placebo Group	Placebo capsules Twice daily	Placebo capsules twice daily	Placebo capsules twice daily	Placebo capsules twice daily	Placebo capsule QHS	No study medication

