Hypothesis 2: Nabilone and XR-NTX will significantly promote abstinence from cannabis use as compared to placebo during the final 2 weeks of study (weeks 11 and 12). The following logistic regression model will be used: (2) logit(Yij = 1) = $\beta 0 + \beta 1$ Ij + $\beta 2$ Uij + ϵ ij where Yij is a dichotomous measure indicating whether the i th subject in the treatment group j has used cannabis during the final 2 weeks of study, with Yij = 1 for non-abstinent and Yij = 0 for abstinent during the final 2 weeks of study; Uij is the vector of all appropriate covariates; Ij is the indicator variable for treatment with nabilone and XR-NTX; and ϵ ij is a random error term. Significant Ij indicates that the odds of abstinence from cannabis during the final 2 weeks are different in each group.

Hypothesis 3: Nabilone and XR-NTX will significantly increase time to dropout as compared to placebo. To test the secondary hypothesis 3, we will use the same model as in (1) to test whether retention is different between the two groups.

Hypothesis 4: Over time, the days of weekly cannabis use will be significantly less in the Nabilone and XR NTX group as compared to the placebo group. This hypothesis will be tested using the following

longitudinal mixed effects model: (3) Yijt = $\beta 0 + \beta 11j + \beta 2t + \beta 3t^*1j + \beta 4Uij + sij + \epsilon ijt$ where Y ijt is the days of cannabis used over a one-week period by the i th subject in the treatment group j at week t (t =1, 2, ..., 12); Uij is the vector of covariates; Ij is the indicator variable for treatment with nabilone and XR-NTX; sij is a random intercept for subject i and ϵijt is a random error term. Significant interaction t*Ij indicates that the effect of each treatment group is different over time (that corresponds to rejecting null hypothesis that $\beta 3= 0$). If so, the effect of time will be estimated for each group separately and the groups will be compared (using contrast) in the last time point t=12. If the interaction term is not significant (i.e., the difference between the treatment arms does not change over time), we will refit the model without the interaction term and test the significance of the main effect of treatment (i.e. rejecting the null hypothesis that $\beta 1 = 0$).

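### The weekly days-of-use model enters a two-day week 1 on the same scale as seven-day weeks, which distorts the treatment-by-time slope when there is a real treatment effect

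*SAP*

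**What the plan says.** SAP 3.e, Hypothesis 4, gives model (3). The outcome is "the days of cannabis used over a one-week period by the i th subject in the treatment group j at week t", observed "at week t (t =1, 2, ..., 12". Week enters as a linear term, treatment and treatment-by-week are fixed effects, and "sij is a random intercept for subject i". There is no offset, denominator or days-at-risk term.

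The interaction is tested first: "Significant interaction t*Ij indicates that the effect of each treatment group is different over time". If it is significant, time is estimated separately in each arm and "the groups will be compared (using contrast) in the last time point t=12". If not, the interaction is dropped and the treatment main effect is tested. On the error level, SAP 3.d says "All tests for main effects will be performed at twotailed significance α =5" per cent; I take the same level for the interaction.

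On the calendar, the protocol's Table 2 (outpatient dosing) labels its first column "Week 1 Days 6-7 (outpatient", and its last column ends week 12 on day 84. Study Procedures describes five inpatient nights and adds "Cannabis relapse measures will begin following discharge on day 6". The same section, citing Table 2, also says that twelve weeks of outpatient treatment come after discharge. The SAP does not map t to study days.

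**The concern.** If weeks are counted as in Table 2, a patient can use cannabis on at most two days in week 1 and on up to seven in every later week. Both arms have the same short week, so at first sight only the common time trend suffers. But a short week also shrinks the difference between arms. If the per-day effect is the same throughout, the week-1 difference in days used is 2/7 of its size in the other weeks. A line fitted through twelve weekly differences, the first of them compressed, tilts upward even when the drug effect per day at risk does not change.

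That tilt is the quantity tested by the interaction term. Under Hypothesis 4 that test selects between the average effect and a contrast at week 12, which closes the four medication-free weeks in Table 2. So the length of the inpatient stay can influence which result is given.

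**Working it through.** **1. Is week 1 really short?** The documents give no power figure for Hypothesis 4, but the payment totals in the protocol's compensation section test the premise. Attendance pay starts at 2.50 and doubles to a cap of 25:

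- 23 visits: 2.50 + 5 + 10 + 20 + 19 x 25 = 512.50; travel 23 x 10 = 230. Both match the stated totals.
- 24 visits (12 full weeks, two visits each): 537.50 and 240. Neither matches.

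Table 3 (outpatient assessments) agrees, with one urine toxicology entry in week 1 and two from week 2.

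**2. Bias in the slope.** With t = 1 to 12, the mean of t is 6.5 and the sum of squares is 143. Let d be the between-arm difference in days per full week. Week 1 shows (2/7)d, a shortfall of (5/7)d.

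- Added slope difference: (1 - 6.5)(-5/7)d / 143 = 0.0275d per week.
- Average difference: (11 + 2/7)d / 12 = 0.940d, 6% too small.
- Fitted difference at week 12: 0.940d + 5.5 x 0.0275d = 1.092d, 9% too large.

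The fit is linear, so with complete data 0.0275 times the full-week week-1 difference is added to whatever slope the true profile has. If d = 0, nothing is added.

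**3. Effect on the interaction test.** SE of the slope difference = SD x sqrt(2/(n x 143)). With n = 40 per arm (SAP A4) this is 0.0280 for SD 1.5 and 0.0374 for SD 2. Neither d nor the residual SD is in the documents; both are assumed. Two-sided 5% rejection for a constant effect:

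| Residual SD | d = 1 | d = 2 |
|---|---|---|
| 1.0 | 31% | 84% |
| 1.5 | 17% | 50% |
| 2.0 | 11% | 31% |
| 2.5 | 9% | 22% |

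With the 36 per arm of SAP 3.b, d = 2 gives 46% (SD 1.5) and 29% (SD 2).

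**4. Simulation of model (3).** 3,000 runs per scenario, 40 per arm, random intercept by REML, beta-binomial days of use, placebo use on 60% of days, 0% or 40% non-informative dropout, covariates omitted (all assumed). The residual SD with the short week came out at about 1.6-1.7.

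- No effect: 3.4-3.7% rejection, so slightly conservative.
- Constant d = 1: 12-13%. Constant d = 2: 41-47%.
- Week 1 dropped: 5.0-5.7% in every scenario, with week-12 contrasts of -0.99 for a true -1 and -2.00 for a true -2.

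**5. If the effect wanes off drug.** Suppose it halves in weeks 9-12. The centred weeks there sum to 2.5 + 3.5 + 4.5 + 5.5 = 16, so the true slope is -0.5 x 16d/143 = -0.056d. The short week moves it to -0.028d. With d = 2, SD 2 and 40 per arm, rejection falls from 85% to 33%. If the effect vanishes in weeks 9-12, the figures are about 100% and 99.5%.

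**The case against.** Several points on the other side have force.

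- **No false benefit.** A reader might infer that the short week manufactures an interaction, or a treatment effect, on its own. It does not: both arms have the same cap, and with no drug effect the expected interaction is zero. This stands fully.
- **A constant effect is doubtful.** Medication is tapered in week 8 and absent afterwards, so waning is plausible. The artefact then makes the switch to the week-12 contrast less likely. Conversely, patients leave the unit abstinent, and a difference that builds as relapses accumulate would be a real interaction. This stands: the direction of the distortion depends on the true profile. The added slope itself needs only a non-zero week-1 difference.
- **The week-1 count is a correct count.** On a days-per-calendar-week scale the smaller difference is real, and the SAP does not say that it wants a rate per day at risk. This stands in part. But the SAP reads the interaction as a treatment effect that changes over time, and here some of it reflects the inpatient stay.
- **The practical shift is small.** Nine per cent is 0.09 to 0.18 days per week for d = 1 to 2. With d = 2 and both SDs assumed to be 2, the main effect has z of about 4.0 and the week-12 contrast about 4.3, so the conclusion would not change. The two-stage rule also exists whatever week 1 looks like.
- **Week numbering is unsettled.** If t counts full weeks from discharge, as the narrative allows, the problem disappears. Table 2, Table 3 and the payments point the other way, but the SAP is silent.
- **Applicability.** Model (3) is written for a nabilone/XR-NTX comparison, and the clonazepam outcome lists (protocol; SAP A2) omit weekly days of use. This lowers the priority. It does not remove the point, because model (3) is the only analysis specified for this outcome.

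**Conclusion.** The point holds conditionally. Under the Table 2 day count, model (3) puts a two-day week beside seven-day weeks, and when there is a real effect this shifts the treatment-by-time slope. The 9% and 6% errors and the 11-17% and 31-50% rejection rates apply to an effect constant in days per week through the medication-free weeks, with assumed d and residual SD. Under waning, the same shift masks part of a true interaction.

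Two stronger readings are not supported. The short week does not raise the false-positive rate for efficacy. It also does not touch the time-to-relapse analysis, because days per week is a secondary outcome in the SAP. Nor is it settled that the analysis weeks follow Table 2; that is the better-supported reading of passages that need reconciling. This is a cheap improvement of low to moderate priority.

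**What to change.** First, state in the SAP which study days make up each analysis week, and reconcile Table 2 (weeks counted from admission, ending on day 84) with the narrative (twelve weeks after discharge). Then choose one of the following in advance:

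- Fit model (3) from t = 2. Cost: two days of data per patient. In the simulation this restored the nominal level and removed the bias.
- Model days used out of days at risk (2 in week 1, 7 afterwards) as a binomial proportion in GLIMMIX, which the SAP already names, allowing for overdispersion. Cost: the effect is no longer in days per week. I have not simulated this.
- Count seven-day weeks from discharge. If follow-up ends on day 84, days 6-84 are 79 days, or 11 full weeks and two days over, so the last time point and the week-12 contrast must be redefined. I have not simulated this either.

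Each is a line or two of SAP text and needs no new data. The natural moment is when model (3) is rewritten for clonazepam.
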